The effectiveness and safety of the early follicular phase full-dose down-regulation protocol for controlled ovarian hyperstimulation: a randomized, paralleled controlled, multicenter trial

2018-12-29

Background

Since the first “tube baby”, Louise Brown, was born in the United Kingdom in 1978, many infertile couples have been benefitted from in vitro fertilization and embryo transfer (IVF-ET) and intracytoplasmic sperm injection (ICSI). It is reported that there are over 5 million babies born with the help of assisted reproductive technology (ART). According to the 2015 national data published by Human Fertility and Embryology Authority (HFEA, 48,147 women received 61,726 IVF/ICSI cycles and gave birth to 17,041 newborns [1]. In the United States, 169,602 IVF/ICSI cycles were performed in 2014 and 68,791 tubal babies were born [2]. China has a huge population base, and therefore has a substantial number of infertile couples. Although a late starter, China is developing rapidly in ART and playing a more and more important role in the area of reproductive medicine.

In spite of the continuous development in ART, so far, the overall success rate of IVF/ICSI is still hovering around 25-40%. The live birth rate per stimulated cycle is 25.6% in the UK in 2015, fluctuating from 1.9% in women aged 45 and elder to 32.2% in women younger than 35 years old [1]. The IVF/ICSI success rate in 2014 in the US is similar [2]. In China, according to the data submitted by 115 reproductive medicine centers on the ART data reporting system developed by Chinese Society of Reproductive Medicine, the delivery rate is about 40% [3]. Hence, there is much room for improvement regarding the live birth rate of IVF/ICSI, which is of great significance to infertile couples.

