There are many factors influencing the success rate of IVF/ICSI, e.g. the infertile couples' age, the controlled ovarian hyperstimulation (COH) protocol, the quality and number of embryos for transferring, the endometrium and luteal phase support protocol, etc. Among them, an appropriate COH protocol is directly associated with the number of oocyte retrieved, as well as the number and quality of embryos, which exert an important influence on the success rate of IVF/ICSI. The luteal phase pituitary down-regulation protocol is one of the most widely used COH protocols in clinical practice, particularly in China. In this protocol, gonadotropin releasing hormone agonist (GnRHa) administered in the previous luteal phase induces a state of down regulation of the pituitary gland via competitive occupying and further exhausting the GnRH receptors in the pituitary, which inhibits the endogenous luteinizing hormone (LH) peak and avoid spontaneous ovulation, decreasing the cycle cancellation rate. But the classic down-regulation protocol may lead to an increased incidence of ovarian hyperstimulation syndrome (OHSS), as well as a negative impact on endometrial receptivity due to the progesterone elevation after multiple oocytes development [4]. The coping strategy is to freeze all the embryos and transfer in the next cycle. Though avoiding the above-mentioned adverse effects, such strategy increases the time to pregnancy (TTP) and therefore results in certain psychological and economic burdens for infertile couples.

In recent years, some Chinese researches applied the early follicular full-dose down-regulation protocol that is always performed to women with endometriosis to a more general IVF/ICSI population and found a clinical pregnancy rate of 64% in the fresh embryo transfer cycle, much higher than that of the luteal phase down-regulation protocol [5-10]. The possible mechanism is that it may improve the down regulation of LH and the endometrial receptivity, therefore having a

better control of LH during COH, increasing the endometrial thickness on hCG day, as well as the embryo implantation rate and clinical pregnancy rate. Furthermore, since this protocol decrease the risk of progesterone elevation on hCG day, it increases the fresh embryo transfer rate and shortens TTP.

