Given most studies regarding the effectiveness and safety of the early follicular phase full-dose down-regulation protocol are retrospective studies, the results may be biased by several confounding factors. Therefore, we would like to conduct a multicenter, randomized controlled trial to compare the pregnancy outcome and safety between the early follicular phase full-dose down-regulation COH protocol and the luteal phase down-regulation protocol.

Methods/Design

We will perform the multicenter, randomized controlled trial in 14 reproductive medicine centers all over mainland China. Included patients will be distributed in a 1:1 ratio to the intervention (early follicular phase full-dose down-regulation) group and the control (mid-luteal phase down-regulation) group. Their live birth rate of fresh embryo transfer and other secondary outcomes will be compared. This study has been approved by the institutional review boards at all study sites. Each participant will sign the consent form before inclusion. Reporting of the study results will follow the 2010 CONSORT statement [11].

Inclusion criteria

The following are the inclusion criteria for this study:

1. Women aged between 20 to 38 years old and with a history of infertility (fail to get pregnant after over one year's regular, unprotected sex), who receive IVF/ICSI for one of the following reasons:
 - ① Tubal factor: e.g. peritubal adhesions, tubal obstruction, etc.. Patients with hydrosalpinx can be enrolled after salpingectomy or tubal ligation;
 - ② Male factor: e.g. oligospermia, asthenozoospermia, teratozoospermia, etc.;
 - ③ Unexplained infertility: patients with a history of infertility more than 1 year but with no specific cause for infertility (ovulation, tubal, endometrial and male factor), or still not get pregnant after the above-mentioned causes being removed.
2. Women with a normal ovarian reserve according to: ① basal steroid hormone on day 2-4 of menstrual cycle: basal FSH≤10mIU/ml, estradiol (E2) <50pg/ml; ② anti-Müllerian hormone (AMH)≥1.1ng/ml; ③ antral follicle count (AFC) ≥7;
3. Women who start their first IVF/ICSI cycle;
4. Women who met the above-mentioned criteria and have given the informed consent.

Exclusion criteria

1. Women with a negative reproductive history, including a history of:
 - ① recurrent miscarriage: women with twice and more than twice spontaneous miscarriage, missed abortion, biochemical pregnancies, etc.;

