For those not receiving a fresh embryo transfer (e.g. due to OHSS), and those not achieving live birth and with surplus cryopreserved embryos, the outcome of frozen-thawed embryo transfer cycles will be followed up and recorded as well.

Outcome measurements

Primary outcome

The primary outcome of this study is live birth rate per transferred cycle, defined as delivery of any viable infant ≥ 28 gestational weeks divided by all transferred cycles.

Secondary outcomes

Secondary effectiveness endpoints will include implantation rate, biochemical pregnancy, clinical pregnancy and ongoing pregnancy. *Biochemical pregnancy* will be achieved if serum β -hCG ≥ 10 U/L. *Clinical pregnancy* is defined as the presence of an intrauterine gestational sac 28 ± 4 days after embryo transfer. Ongoing pregnancy is defined as a viable pregnancy at 10-12 gestational week. The safety endpoints will include moderate and severe OHSS, pregnancy loss, pregnancy complications, neonatal birth weight and adverse fetal outcomes (e.g. malformation, intrauterine fetal death, etc.)

Statistical analysis

Sample size and power calculation

Sample size will be calculated based on superiority test. The significance level will be set at $\alpha = 0.05$ and the statistical power will be set as $1 - \beta = 0.80$. The reported live birth rate is about 30%, while the live birth rate of the prolonged protocol is predicted to be around 40% based on previous retrospective studies. We set the delta value as 6%, and the ratio between groups will be 1:1; therefore, the sample size of each group is 851. Taking into consideration a drop rate of 10%, we expect to ultimately have a total of 1892 enrollees, with 946 participants in each group.

Statistical analysis method

1. Statistical description: We will adopt descriptive statistical analysis to summarize the participants' demographic characteristics, physical examination, laboratory tests, other health information and the outcome indicators. The continuous variables will be described with means and standard deviation (or median and interquartile range), while the categorical variable will be described with frequency and percentage. The proportion of drop-off cases will be calculated and analyzed.

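### The stated 80% power with 851 per group is not reproduced at the plan's own 30% control rate, which is unsourced and not reconciled with the 40% Chinese delivery rate in the Background

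*Combined protocol and SAP*

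**What the plan says.** The section on sample size and power calculation says: "Sample size will be calculated based on superiority test". It sets the significance level at 0.05 and power at 0.80, without saying whether the test is one- or two-sided. On the rates it says: "The reported live birth rate is about 30%, while the live birth rate of the prolonged protocol is predicted to be around 40" per cent, the latter from retrospective studies. It then sets delta at 6% with 1:1 allocation, arrives at 851 per group, and allows 10% for dropout to reach 946 per group and 1892 in total. It gives no citation or denominator for the 30% and does not say what the 6% stands for.

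The Background has several figures that bear on the control rate. For 115 Chinese centres, "the delivery rate is about 40" per cent, with no denominator. For the UK, the live birth rate is 25.6% per stimulated cycle over all ages, and "32.2% in women younger than 35 years old". Overall success is put at 25-40%. For the new protocol, Chinese studies "found a clinical pregnancy rate of 64% in the fresh embryo transfer cycle", which is a different endpoint.

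The trial runs in 14 centres in mainland China. It enrols women aged 20 to 38 with normal ovarian reserve ("Women who start their first IVF/ICSI cycle" is a criterion). The primary outcome is live birth per transferred cycle.

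**The concern.** A power statement can be checked only if the control rate, the difference, the role of that difference and the sidedness are all known. Here the control rate has no source, and the other two points are left open. The predicted rates differ by 10 points while delta is 6, so a reader cannot tell whether 6 points is the smallest difference to be detected or a margin to be exceeded.

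The control rate raises a further question. The only Chinese figure in the document is about 40%, and the 30% lies closer to the UK figures. The UK all-ages figure is explicitly per stimulated cycle, and the under-35 figure appears to share that denominator. The trial counts only transferred cycles in a selected population, so 30% may be low for its control arm. The plan does not discuss this.

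What is at stake is how the result is read. If the trial finds no significant difference, readers will judge that against the claimed 80% power, so the claim needs to be right for a stated difference and test.

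**Working it through.** **Inputs.** From the sample-size section: significance level 0.05, power 0.80, rates 30% and 40%, delta 6%, 851 per group, dropout 10%. From the Background: 40%. Control rates of 35%, 45% and 50% are assumed for illustration, because the documents give no per-transfer rate for this population.

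**Formulas.** With d = p2 − p1, p̄ = (p1 + p2)/2, A = √[2p̄(1 − p̄)] and B = √[p1(1 − p1) + p2(1 − p2)]:

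- n per group = (zα·A + zβ·B)² / d²
- power = Φ[(d·√n − zα·A) / B]
- with a superiority margin m: power = Φ[(d − m)/(B/√n) − zα], and n = (zα + zβ)²·B² / (d − m)²

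zα is 1.960 two-sided or 1.645 one-sided; zβ = 0.842.

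**Step 1: the plan's own 851.** The dropout step reproduces: 851/0.9 = 945.6, so 946, and 2 × 946 = 1892. The 851 does not. At 80% power:

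| Reading | n per group, two-sided 0.05 | n per group, one-sided 0.05 |
|---|---|---|
| 30% vs 36% | 963 | 759 |
| 30% vs 40% | 356 | 281 |
| 30% vs 40%, 6-point margin | – | 1739 |

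The margin reading needs 2208 at one-sided 0.025. Continuity correction moves the first two rows to 996/792 and 376/300. None of these is within 3% of 851.

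Near matches need inputs that the plan does not state. 40% vs 46% one-sided gives 841, and 30% vs 24% two-sided gives 859, in the wrong direction for superiority. One mixture rounds to 851: (1.645 + 0.842)² × (0.21 + 0.2304)/0.04²/2 = 850.9. It takes the variance from 30% and 36%, the net difference from 30% vs 40% less 6 points, a one-sided test, and half of the result. Nothing in the plan supports that combination, so I do not treat it as the derivation.

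**Step 2: power of 851 at the plan's 30%.** √851 = 29.172.

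- 30% vs 36%: A = √0.4422 = 0.6650, B = √0.4404 = 0.6636, d√n = 1.7503. Two-sided: (1.7503 − 1.3033)/0.6636 = 0.674, power 75.0%. One-sided: (1.7503 − 1.0938)/0.6636 = 0.989, power 83.9%.
- 30% vs 40%: A = √0.455 = 0.6745, B = √0.45 = 0.6708, d√n = 2.9172. Two-sided: (2.9172 − 1.3221)/0.6708 = 2.378, power 99.1%.
- 30% vs 40% with a 6-point margin: B/√n = 0.0230. One-sided 0.05: 0.04/0.0230 − 1.645 = 0.095, power 53.8%.

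No reading gives 80%.

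**Step 3: a higher control rate, 851 per group, 6-point gain.**

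| Control vs intervention | Two-sided 0.05 | One-sided 0.05 |
|---|---|---|
| 30% vs 36% | 75.0% | 83.9% |
| 35% vs 41% | 72.3% | 81.8% |
| 40% vs 46% | 70.6% | 80.4% |
| 45% vs 51% | 69.8% | 79.8% |
| 50% vs 56% | 69.9% | 79.9% |

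The difference detectable with 80% two-sided power is about 6.4 points at 30% control and 6.7 at 40%. A 10-point gain keeps about 99% two-sided power at either rate (99.1% at 30%, 98.6% at 40%). With a 6-point margin and a 10-point gain, one-sided power at 40% control is 50.9%.

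**Step 4: where the shortfall comes from.** Two-sided, 6 points, 40% control: 80 − 70.6 = 9.4 points short. Of these, 80 − 75.0 = 5.0 are already there at 30%, and 75.0 − 70.6 = 4.4 come from the control rate. Sidedness alone moves power by 83.9 − 75.0 = 8.9 points at 30%. The role of the 6% moves it from about 99% to about 54%.

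**The case against.** The strongest reply is that 30% is an ordinary planning assumption. It lies inside the 25-40% range in the Background. The Chinese 40% is a delivery rate from a reporting system, with no denominator, age mix, protocol mix or split between fresh and frozen transfers. A reader might infer that it contradicts the 30%. It does not: the two figures are in tension, and neither is shown to be the per-transfer rate for this control arm. This part of the objection stands.

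The reply continues that a one-sided test at 0.05 meets the claim for a 6-point gain at 30% (83.9%) and at 40% (80.4%). That also stands, but the plan does not state a one-sided test, so it supports asking for the sidedness.

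A reader might also note that the predicted 40% equals the national figure and infer that there may be no gain to find. Holding the intervention at 40% while the control rate rises gives two-sided power of 56.8% at 35% control and 13.3% at 38%. The documents do not support that scenario. Selection of patients and the per-transfer denominator apply to both randomized arms, so an argument that raises one rate would tend to raise the other. The Background reports a much higher clinical pregnancy rate with the new protocol than with the luteal one.

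What the objection does not answer is that 0.80 is not reproduced at the plan's own 30%, and that the 30% has neither source nor denominator.

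**Conclusion.** The point holds as a fault in the stated power and its inputs. With 851 per group, a 6-point gain from 30% has 75.0% power on a conventional two-sided reading, against the stated 80%. At control rates of 40-50% it has about 70%. One-sided at 0.05, the claim is met at 30% and 40% and missed by about 0.2 points at 45-50%.

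The control rate is not the main cause. At 40% it accounts for 4.4 of the 9.4 missing points two-sided, and the unstated sidedness and undefined delta matter more. The documents support neither a finding that the 30% is wrong nor one that the treatment effect may be absent.

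The figures assume a simple comparison of two proportions with 851 analysable women per group, without covariate adjustment. The two-sided test is my reading, and control rates above 30% are a range to examine; the documents do not establish them for this arm.

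**What to change.** Rewrite the paragraph under the sample size and power calculation as follows:

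1. State whether the 0.05 is one- or two-sided.
2. State whether 6% is the difference to be detected or a superiority margin, and how it relates to the predicted 30% and 40%.
3. Give the source of the control rate and its denominator, on the per-transfer basis of the primary outcome, and explain why it differs from the 40% in the Background.
4. Replace the single 0.80 with the power that 851 per group gives over control rates of 30-50%, labelled as an assumed range. For a 6-point detectable difference this is 75% to 70% two-sided. If a one-sided test or a margin was intended, report the matching figures instead: about 84% to 80% for a one-sided 6-point difference, or about 54% at 30% vs 40% with a 6-point margin at one-sided 0.05.

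The cost is one rewritten paragraph and, on the two-sided reading, a less favourable power figure. Enrolment need not change.

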2) *Control group* (luteal phase long down-regulation group)

Patients have an injection of short-acting triptorelin acetate (Decapeptyl®, Ferring, Germany) 0.1mg every day, 10-12 days before the menstruation and receive the endocrinology and ultrasound examinations 14-21 days thereafter. If complete pituitary down-regulation is achieved (endometrial thickness≤5mm, basal FSH≤5mIU/mL, LH≤5mIU/mL, E2≤50pg/mL) and the diameter of follicles between 4-6mm under ultrasound,

a supplementation of recombinant FSH (Gonal-F®, Merck, Switzerland) will be given according to the participants' BMI ($18 \leq \text{BMI} \leq 22$, starting dose 112.5IU/d; $22 < \text{BMI} \leq 25$, starting dose 150IU/d).

2. *Ovarian response monitoring and gonadotropin dose adjustment:* 4 days after the daily injection of rFSH, the physician will perform ultrasound to monitor the follicular growth, measure the serum hormone level and adjust the dose of exogenous gonadotropins accordingly.

Trigger and oocyte retrieval

1. *hCG trigger for final oocyte maturation:* When the desired follicle size is reached (at least one follicle ≥ 19 mm or two follicles ≥ 18 mm or three follicles ≥ 17 mm), 250 μ g recombinant human chorionic gonadotropin (HCG) (Luveris®, Merck, Switzerland) will be administered subcutaneously.
2. *Oocyte retrieval:* Oocyte retrieval will be performed transvaginally 36-38 hours after pre-ovulatory hCG injection under ultrasound monitoring.
3. *In vitro fertilization and embryo culture:* Oocyte retrieved will be cultured in vitro for 3-6h before being fertilized via IVF or ICSI. Two top-quality Day 3 cleavage embryos will be transferred 72h after retrieval. If more than 15 oocytes are retrieved, the participant should receive ultrasound examination on the day of embryo transfer. For those complaining abdominal or stomach distension, with an ovary ≥ 7 cm in diameter, estradiol ≥ 4500 pg/ml, there is a high risk of developing moderate or severe OHSS, and all the embryos should be frozen.

Embryo transfer and luteal phase support

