2. Comparable analysis It will be used to compare the demographic and other baseline characteristics to make sure the comparability of the two groups. If the continuous variables follow the normal distribution, t test will be performed; if not, the rank sum

test or a normal transformation will be performed. For the categorical variables, chi-square test or Fisher's exact test will be performed.

3. Statistical analysis for the outcome measures Between-group differences for categorical and continuous outcome variables will be assessed by logistic regression and linear regression, respectively.
4. Safety analysis: Adverse events and reaction will be listed and analyzed using the chi-square test.
5. The analysis for the primary outcome and important outcome measurements will be based on both the intention-to-treat analysis and per-protocol analysis. The results of these two analyses will be compared in the final analysis.

Reference

- [1] The United Kingdom national data. Human Fertility and Embryology Authority. 2015
- [2] The United States national assisted reproductive technology(ART) data. Centers for Disease Control and Prevention.2015
- [3] Chinese Reproductive Medicine Society national assisted reproductive technology (ART) data. 2015
- [4] L Hu, Y Sun. The impact of various controlled ovarian hyperstimulation (COS) protocols on the outcome of in vitro fertilization and embryo transfer (IVF-ET). *Journal of Practical Obstetrics and Gynecology*. 2014;30(10):723-725.
- [5] Y Hu, T Ding, Y Zhao, Q Wu. The comparison of the birth outcome of in vitro fertilization and embryo transfer (IVF-ET) after two different down-regulation protocols. *Maternal and Child Health Care of China*.2017;32(4):808-810.
- [6] D Xu, Q Wu. The comparison of the application of ultra-long down-regulation protocol and antagonist protocol in in vitro fertilization and embryo transfer (IVF-ET). *Jiangxi Medical Journal*. 2015;50(1):13-15.
- [7] Q Su, Q Wu, L Tian, Y Li. The clinical analysis of different controlled ovarian hyperstimulation (COS) protocols in in vitro fertilization and embryo transfer (IVF-ET). *Jiangxi Medical Journal*. 2014;49(8):723-725.
- [8] Y Li, Q Wu, Y Yi. The impact of the follicular phase ultra-long long down-regulation protocol on PCOS patients' outcome after in vitro fertilization and embryo transfer (IVF-ET). *Jiangxi Medical Journal*. 2014;49(2):117-120.

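### The 851 per group does not follow from the stated sample-size inputs, because delta, sidedness and formula are not given; the power it delivers depends on which reading was meant

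*Combined protocol and SAP*

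**What the plan says.** All the sample-size inputs stand in one paragraph, Sample size and power calculation:

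- The hypothesis: "Sample size will be calculated based on superiority test". Alpha is 0.05 and power 0.80. Whether the test is one- or two-sided is not stated.
- The rates: about 30% as reported, and around 40% forecast for the intervention from retrospective data.
- The result, which brings in delta: "We set the delta value as 6%, and the ratio between groups will be 1:1; therefore, the sample size of each group is 851".
- The dropout step: a 10% allowance raises this to 946 per group, 1,892 in all.

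Statistical analysis method, item 3, gives the analysis: "Between-group differences for categorical and continuous outcome variables will be assessed by logistic regression and linear regression, respectively". It names no margin and no sidedness. Item 5 plans both intention-to-treat and per-protocol analyses and does not say which one the sample size serves.

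The endpoint is defined under Primary outcome: "The primary outcome of this study is live birth rate per transferred cycle".

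**The concern.** The paragraph holds two effect sizes. The rates imply 10 points; delta is 6. It presents 851 as the consequence of all the inputs together without saying what delta does. It could be the difference to detect, in which case one of the two rates plays no part. It could also be a superiority margin, in which case all three figures are used. These readings lead to very different sample sizes.

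What is at stake is the 80% power attached to 851. A reader of the final report, particularly after a non-significant result, needs to know which difference the trial had a good chance of detecting. As written, the protocol does not tell them, and the figure cannot be checked.

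**Working it through.** **Inputs.** From Sample size and power calculation: alpha 0.05, power 0.80, 30%, 40%, delta 6%, 1:1, dropout 10%. Sidedness is not given, so both versions are shown.

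**The plan's own dropout step.** 851/0.9 = 945.6, rounded up to 946; 2 × 946 = 1,892. This reproduces. The difficulty lies in the 851 alone.

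**Formulas (per group).**

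- Unpooled: n = (z_α + z_0.80)² × [p1(1−p1) + p2(1−p2)] / (d − m)², where d = p2 − p1 and m is the margin (0 if none). The squared term is 7.849 two-sided and 6.183 one-sided.
- Pooled: n = [z_α√(2p̄(1−p̄)) + z_0.80√(p1(1−p1) + p2(1−p2))]² / d², where p̄ is the mean of the two rates.
- Continuity-corrected: n′ = (n/4) × [1 + √(1 + 4/(nd))]², applied to the pooled n.

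**Worked examples (unpooled, two-sided).**

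- 30% v 40%: 7.849 × (0.21 + 0.24)/0.10² = 353.2, so 354.
- 30% v 36%: 7.849 × (0.21 + 0.2304)/0.06² = 960.2, so 961.
- 30% v 40% with a 6% margin: 7.849 × 0.45/0.04² = 2,207.5, so 2,208.

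**Required per group for 80% power (unpooled / pooled / continuity-corrected).**

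| Reading | Two-sided 5% | One-sided 5% |
|---|---|---|
| 30% v 40%, no margin | 354 / 356 / 376 | 279 / 281 / 300 |
| 30% v 36% | 961 / 963 / 996 | 757 / 759 / 792 |
| 34% v 40% | 1,013 / 1,016 / 1,049 | 798 / 800 / 833 |
| 30% v 40%, margin 6% (unpooled) | 2,208 | 1,739 |

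No entry is 851.

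**Near matches that use a rate the paragraph does not give.**

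- 34% v 40%, one-sided, continuity-corrected (in the table above): 833.
- 40% v 46%, one-sided: 839 / 841 / 874.
- 24% v 30%, two-sided: 856 / 859 / 892.

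**Power with 851 per group and no margin.** Power = Φ{[d√n − z_α√(2p̄(1−p̄))] / √(p1(1−p1) + p2(1−p2))}.

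| Rates | Two-sided 5% | One-sided 5% |
|---|---|---|
| 30% v 40% | 99.1% | 99.6% |
| 30% v 36% | 75.0% | 83.9% |
| 34% v 40% | 72.7% | 82.1% |
| 30% v 36.4% | 80.1% | 87.7% |

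A simulated two-sided Wald test of the log odds ratio, which stands in for the planned logistic regression, gives 99.1%, 75.0%, 72.7% and 80.0% for the same four rows. If all 946 per group are analysed at the same rates, two-sided power is 79.3% for 30% v 36% and 77.2% for 34% v 40%.

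**Power with 851 per group if 6% is a superiority margin, 30% v 40%.** 0.04/√(0.45/851) = 1.739. Two-sided: Φ(1.739 − 1.960) = 41%. One-sided: Φ(1.739 − 1.645) = 54%.

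**The case against.** The strongest reply is that some sensible calculation probably lies behind 851. The closest candidate with the intervention arm higher is 40% v 46%, one-sided, at 839 to 874. The Background does give a delivery rate of about 40% for Chinese centres, and 851 would have slightly over 80% power for that pair. It remains a guess: the sample-size paragraph gives about 30% as the reported rate, assigns 40% to the intervention and never mentions 46%. The other near matches also swap a stated rate for an unstated one, and none of the formulas above returns 851 for any of them. That several incompatible guesses land close by is a reason to recover the original inputs, not to pick one.

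A second reply is that the shortfall for 6 points depends on two-sided testing, which the documents do not specify. That stands. At one-sided 5%, 851 gives 82-84% for 6 points, which is above 80%.

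A third is that the planned logistic regression has no margin, so the 41-54% figures are beside the point. This holds for what will be tested. It does not show what the sample-size calculation assumed, and the margin reading is the only one in the first table that uses 30%, 40% and 6% together.

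A reader might also infer that the trial is underpowered, or that the protocol promises 80% power for a 6-point difference. The documents support neither. At the stated rates, without a margin, power is over 99%. The 80% stands beside an undefined delta and is never tied to 6 points.

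**Conclusion.** The point holds as a defect of derivation and reporting. The 851 does not follow from the inputs from which the protocol says it follows, and no other section resolves this. The consequence depends on facts that the documents do not give:

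- no margin, 30% v 40%: far more than 80% power, whether one- or two-sided;
- no margin, 6 points: short of 80% by 5 to 7 points if two-sided, above it by 2 to 4 points if one-sided;
- 6% as a margin at 30% v 40%: well short of 80%, with a planned analysis that does not test the margin.

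All these figures assume 851 women per group in the analysed denominator. The sample size counts participants, while the endpoint counts transferred cycles, and the protocol foresees women without a fresh transfer. Under Trigger and oocyte retrieval, item 3, it says of some that "there is a high risk of developing moderate or severe OHSS, and all the embryos should be frozen". The protocol gives no rate for this and does not say whether the 10% dropout covers it, so the effect is not quantified here.

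This should be fixed. It is not a reason to change enrolment under the planned no-margin test.

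**What to change.** 1. Recover from the original calculation, rather than choosing afterwards, what delta meant, the two rates, the sidedness and the formula. State them under Sample size and power calculation.
2. Then replace the claim of 80% power at 851 with the power delivered under those inputs. If they prove to be two-sided 5% without a margin, the text could read: with 851 analysed per group, power is about 99% for 30% v 40%, 75% for 30% v 36% and 80% for 30% v 36.4%; if all 946 per group are analysed, power for 30% v 36% is about 79%.
3. State that these figures assume 851 or 946 in the analysed denominator, given that the primary outcome is per transferred cycle, and which analysis set they refer to.
4. Only if a superiority margin was used, make the primary test match it by comparing the lower confidence limit of the risk difference with 6 points, and report the 41% (two-sided 5%) or 54% (one-sided 5%) power at 30% v 40%.

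The cost is protocol and SAP wording, with no extra patients. The downside is that the stated power may become less favourable, depending on what the recovered inputs turn out to be.
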